STUDY PROTOCOL PLAN AND STADISTICAL ANALYSIS PLAN (SAP)

UNIVERSITY CEU CARDENAL HERRERA

Principal investigator: [name] [name]

TITLE: Stabilometric and baropodometric evaluation of osteopathic scaphoid tug manipulation

Research and Ethics Committee of CEU Cardenal Herrera University Number: CEEI22/322

NCT ID: [not yet assigned]

DATE: 10/13/2022

STUDY PROTOCOL PLAN

Objectives:

The objectives of our study have been the following:

General:

The main objective of this study was to evaluate, in healthy individuals, the stabilometric and baropodometric modifications recorded after an osteopathic tug manipulation of the scaphoid, neurophysiologically related to the static and postural control system of the body (exocaptor input) and biomechanically as a structure that communicates the body with the ground

Specific:

To evaluate by means of stabilometry the modifications in the variables of oscillation in X axis, oscillation in Y axis and ellipse area between the intervention group and the control group after the performance of an osteopathic scaphoid tug manipulation or a placebo technique respectively and to evaluate the results.

To assess the changes in the variables % weight load, bearing surface and maximum pressure in both feet by baropodometry between the intervention group and the control group after the application of a scaphoid tug manipulation or a placebo manoeuvre respectively and to compare the results.

To study and compare the results of the stabilometric and baropodometric variables obtained between the subgroups of the intervention group after the osteopathic tug manipulation of the scaphoid: audible and non-audible manipulation and to compare the results.

Volunteers who want to participate in the study will read the general information of the study and sign the informed consent to participate in the study.

Once the informed consent has been read and delivered, the evaluator will check that they meet the inclusion criteria. After the data collection, a randomization (Epidat V4.0) of the selected subjects will be carried out to assign them to one of the intervention groups.

The sequence of the study was as follows:

1. Information about the study to the subjects likely to participate.
2. Provision of the informed consent form to be read and signed by the patient (appendix I).
3. The evaluator will take the data for the clinical history.
4. The assessor will evaluate the mobility of the scaphoid of the right foot and will verify that it is in osteopathic external rotation dysfunction, if this dysfunction is not present, the subject will be excluded from the study.
5. The assessor shall collect data to obtain the independent variables of stabilometry and baropodometry by means of standardised recording on the measurement platform in a standardised room for this purpose.
6. The patient will go to an adjoining room with the auditor to carry out the randomisation process (random number generator) and thus classify the patient into the experimental or control group.
7. Implementation of the intervention: in the experimental group, the scaphoid tug technique will be performed. In the control group patients a sham technique will be applied.
8. The patient will return to the assessment room with the assessor for data collection to obtain the variables of stabilometry and baropodometry by standardised recording on the measurement platform, as was done previously.

9. Collection of data on computer support by means of a database.

Baropodometric and stabilometric assessment:

Stabilometric and baropodometric assessment was carried out using this sequence:

- The subject should be dressed in comfortable clothing and barefoot on the measuring platform.
- Upright position with arms relaxed.
- Placement of a wooden pattern for the positioning of the patient's feet, instructing him to place his feet against the edges of the wooden pattern and the heels subsequently contacting the guide (heel separation 2 cm and separation of 30°). Once positioned, the wooden pattern is removed.
- Stabilometric measurements and recordings: this shall be taken before the baropodometric recording, with a recording time of 51 seconds 2 tenths (standardised and consensual recording time).
- Measurement and baropodometric recording: this recording shall be performed after the stabilometric recording while maintaining the same posture.

The stabilometric evaluation will be carried out with the eyes open, as only the foot sensor will be evaluated in the study.

The stabilometric scan of this study will provide the following data:

- Oscillation about the X-axis.
- Y-axis oscillation.
- Area of the ellipse.

The static baropodometric scan of this study shall provide the following data:

- Area of support of the foot.
- Percentage of body load supported by each foot.
- Point of maximum plantar pressure.

Scaphoid mobility assessment.

Scaphoid mobility will be assessed by means of a manual mobility test, for which the eversion restriction of the first ray of the foot will be evaluated: patient lying supine on the stretcher, the assessor standing at the patient's feet, then takes the internal arch with one hand in a duckbill and with the other hand fixes the rearfoot at 90°, once the sockets are fixed he checks the direction of the restriction by performing a compression to test the talus-scaphoid and a lighter axial compression to test the first wedge-scaphoid joint. If there is restriction of scaphoid inversion or internal rotation movement, the test is positive, indicating that the scaphoid is in an osteopathic external rotation lesion.

Osteopathic tug manipulation of the scaphoid.

The aim of the scaphoid tug technique is to act on the scaphoid inferiority and external rotation lesion, releasing the scaphoid joint restriction in external rotation, correcting the possible flattening of the plantar vault and thus relaxing the possible hypertonia of the posterior tibialis.

The sequence of execution of the scaphoid tug technique shall be as follows: patient in the supine position, the intervener in a double feint at the patient's feet facing the patient's head, slightly oblique to the outside. The inner hand of the intervener makes contact with the pisiform through the hypothenar eminence and ulnar border of the hand over the scaphoid tubercle, the outer hand reinforces the contact. The thumbs are directed to the sole of the patient's foot. The parameters are sought by bringing the sole of the foot into eversion, thus bringing the scaphoid into internal rotation, i.e. in the direction of correction. To reduce the slack, the operator drops his body weight backwards while increasing the internal rotation parameter of the scaphoid. The

manipulation is performed by associating a rapid traction movement with an increase of the correction parameter towards scaphoid internal rotation.

Statistical Analysis Plan (SAP)

A descriptive and exploratory analysis of the variables of interest will be carried out in order to detect anomalous cases and to clean the database. The assumption of normality will be tested with the Shapiro-Wilks test in combination with an analysis of Q-Q and Q-Q normality plots without trend. The assumption of equality of variances will be tested with Levene's test. A repeated measures ANOVA model will be applied with the variable of interest as the within-subjects factor (three levels) and the group as the between-subjects factor (two levels). Bonferroni correction will be used for two-to-two comparisons. Effect size will be estimated with Cohen's d (1988) where values around 0.20 will be considered small effect size; around 0.50 moderate and 0.80 or higher, large. The statistical analysis software used will be IBM SPSS Statistics 24.0 (SPSS Inc. IBM Company, 2010) and a 95% confidence interval will be applied in all statistical tests.

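### Nothing about foot pain or any other reaction is recorded after the thrust or sham, so the trial cannot report on harm or recognise guarding of a sore foot as a possible explanation for its results

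*Combined protocol and SAP*

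**What the plan says.** The visit is set out in the Study Protocol Plan as nine numbered steps. Apart from consent, the only step that takes information from the participant is step 3, before any intervention: "The evaluator will take the data for the clinical history". At step 4, "The assessor will evaluate the mobility of the scaphoid of the right foot"; no other foot is mentioned, so a right-foot technique is the natural reading. Step 5 takes the baseline platform recordings and step 6 randomises.

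Step 7 applies the technique. The section on the osteopathic tug manipulation says that the operator takes up the slack with body weight and that the "manipulation is performed by associating a rapid traction movement with an increase of the correction parameter towards scaphoid internal rotation". For the comparator the text says only: "In the control group patients a sham technique will be applied".

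Step 8 reads: "The patient will return to the assessment room with the assessor for data collection to obtain the variables of stabilometry and baropodometry". The baropodometric and stabilometric assessment section lists six outputs: X oscillation, Y oscillation, ellipse area, support area, maximum plantar pressure and "Percentage of body load supported by each foot". Step 9 is entry into the database.

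The general objective is to evaluate, "in healthy individuals, the stabilometric and baropodometric modifications recorded after an osteopathic tug manipulation of the scaphoid", a structure described as "neurophysiologically related to the static and postural control system of the body (exocaptor input") and also, in the same sentence, as a biomechanical link between body and ground.

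The SAP specifies a repeated measures ANOVA with group as the only between-subjects factor, screening for anomalous cases, and Cohen's d read against 0.20, 0.50 and 0.80. Neither the protocol nor the SAP mentions pain, soreness, symptoms, adverse events or safety.

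**The concern.** Two things are at stake.

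The first is harm. Healthy volunteers receive a rapid thrust to the foot, and the visit ends without anyone recording whether it hurt or caused any other reaction. Analysts cannot recover that information later. The report could not state that no reactions occurred, only that none were recorded.

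The second is interpretation. Shortly after the technique, the participant stands barefoot for 51.2 seconds of stabilometry and then holds the same posture for baropodometry. A person protecting a sore foot may load it less, and percentage load per foot responds directly to that. Support area, maximum pressure and sway may change too. Guarding is neither of the routes named in the objective, and no recorded variable would reveal it. The planned comparison of audible with non-audible manipulations lies wholly within the manipulated arm, so the sham group offers it no protection.

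**Working it through.** **Check 1: is anything recorded after the intervention besides platform data?** The steps in order:

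- Steps 1-3: information, consent, clinical history. All precede the intervention.
- Step 4: manual mobility test of the right scaphoid. Before the intervention.
- Step 5: baseline platform recordings. Before the intervention.
- Step 6: randomisation.
- Step 7: thrust or sham.
- Step 8: platform recordings repeated as at baseline, giving the six listed outputs.
- Step 9: data entry.

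Only steps 8 and 9 follow the technique, and neither includes a question to the participant. The SAP has no symptom variable. Its screening for anomalous cases is not linked to symptoms, so it would not identify soreness and might remove such a participant without a recorded reason. The omission is confirmed on the supplied text.

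**Check 2: how large could a guarding component be?** The plan states no figure to reproduce: it gives no sample size, SD or event rate. The inputs below are therefore assumptions, chosen to show a range.

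- Share of the manipulated arm that is sore: p = 0.10 to 0.30.
- Load shifted off the foot by a sore participant: s = 3 to 10 percentage points.
- SD of change without soreness: σ = 3 to 5 points.
- No soreness in the sham arm, and arms of equal size.

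Mean difference from guarding alone = p × s.

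- Low: 0.10 × 3 = 0.3 points.
- High: 0.30 × 10 = 3.0 points.

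A mixture of sore and non-sore participants also widens the spread in the manipulated arm. Added variance = p(1 − p)s², so the pooled variance is σ² + ½p(1 − p)s², and d = ps / √(σ² + ½p(1 − p)s²).

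- Low end, σ = 5: added variance 0.10 × 0.90 × 9 = 0.81; pooled variance 25 + 0.405 = 25.405; SD 5.04; d = 0.3 / 5.04 = 0.06.
- High end, σ = 3: added variance 0.30 × 0.70 × 100 = 21; pooled variance (9 + 30) / 2 = 19.5; SD 4.42; d = 3.0 / 4.42 = 0.68.
- High end, σ = 5: pooled variance (25 + 46) / 2 = 35.5; SD 5.96; d = 3.0 / 5.96 = 0.50.

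d rises with p and with s and falls with σ, so 0.06 and 0.68 are the extremes over these ranges. On the SAP's scale that runs from well below a small effect to above a moderate one, but short of 0.80. If no one is sore, the component is zero.

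**The case against.** The strongest reply is that soreness caused by the manipulation, and any unloading that follows from it, are part of what the manipulation does. The randomised comparison then estimates the total effect on load, pressure and sway correctly. The specific objectives ask for just such group comparisons, and no analysis in the SAP tests a mechanism. This stands. What is uncertain is the explanation of a difference, not the difference itself.

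A reader might infer that the plan would report soreness as a postural-control effect. The documents do not support that. Nothing in them says that soreness occurs, and the general objective names a biomechanical route as well as the neurophysiological one. The sham is not described, so it may cause similar discomfort and some of the effect may cancel between arms.

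A reader might also divide 3.0 points by an SD of 3 and call the effect large, at d = 1.0. That standardises by the SD without soreness. With 30% shifting 10 points, the mixture alone has an SD of √21 = 4.6, so the manipulated arm cannot have a total SD of 3.

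Finally, the consent form (appendix I) and the clinical-history form are not in the supplied text, so other reporting arrangements cannot be excluded. Neither is a step that records reactions after the technique, so the omission from the visit sequence remains.

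**Conclusion.** The point holds in this form: the visit sequence and the SAP record nothing about pain or any other reaction after the thrust or sham. As written, the trial can report nothing on harm. Guarding of a sore foot would be an unmeasured possible explanation for a group difference, inseparable from the two routes in the objective.

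The omission is certain on the supplied text. Its effect on interpretation is not. The range of 0.06 to 0.68 rests entirely on the assumed soreness rate, load shift and SD, and on a sham arm without soreness. It shows only that the possibility runs from negligible to more than moderate, with nothing recorded to tell which. It is not evidence of bias and does not invalidate the randomised comparison. The change is worth making because it is cheap and the information cannot be obtained afterwards.

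**What to change.** At step 8, only after both the stabilometric and the baropodometric recordings have been saved, have the existing assessor ask every participant, in the same words in both arms:

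- current pain in the right foot and in the left foot, each on a 0-10 scale;
- whether any pain is new since the technique;
- whether there has been any other reaction.

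Do not put a pain question between the baseline recording and the step 8 recording. It would direct attention to the foot and could influence the second measurement in both arms.

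Add to the SAP: pain and reactions reported by group; platform outcomes described by presence or absence of new pain, as a descriptive check only; and guarding named as a possible explanation if new pain is more common in the manipulated arm.

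The cost is about a minute per visit, with no extra staff or device. There are two limitations. Baseline pain is recalled rather than measured. The new-pain subset is formed after treatment, so it supports no causal conclusion and cannot decide which explanation is right.

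### Does the scaphoid mobility test need a combining rule for its two joints, a graded threshold and a second reader before the trial can rest on it?

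*Combined protocol and SAP*

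**What the plan says.** Step 4 of the study sequence has the assessor examine the right scaphoid and "verify that it is in osteopathic external rotation dysfunction, if this dysfunction is not present, the subject will be excluded from the study". The protocol refers to inclusion criteria but lists none, so this is the only entry test it spells out.

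The section on scaphoid mobility assessment describes a manual test in which "the eversion restriction of the first ray of the foot will be evaluated". The assessor finds the direction of restriction by "performing a compression to test the talus-scaphoid and a lighter axial compression to test the first wedge-scaphoid joint". The result is then given in one sentence: "If there is restriction of scaphoid inversion or internal rotation movement, the test is positive".

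The section on the manipulation says "The aim of the scaphoid tug technique is to act on the scaphoid inferiority and external rotation lesion", and describes the set-up as "bringing the sole of the foot into eversion, thus bringing the scaphoid into internal rotation, i.e. in the direction of correction". The general objective is "to evaluate, in healthy individuals, the stabilometric and baropodometric modifications recorded after an osteopathic tug manipulation of the scaphoid".

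Step 5 records the platform variables at baseline and step 6 randomises. After the intervention, step 8 provides for "data collection to obtain the variables of stabilometry and baropodometry by standardised recording on the measurement platform, as was done previously". Nothing in the protocol or SAP mentions a second reader, a repeat of the mobility test or an agreement statistic.

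**The concern.** The positivity sentence uses the word or to join two movements, not two joints. A foot restricted at the talus-scaphoid joint but free at the first wedge-scaphoid joint has no stated classification. No grade, angle or comparison says what counts as restricted. One person decides, by hand, in healthy volunteers, and the data listed at steps 5 and 8 do not include the screening result.

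The stake would be dilution. If the technique works by acting on the lesion, a foot admitted without the lesion has nothing to act on and pulls the difference between arms toward zero. A null result could then mean that the technique does nothing, or that too few enrolled feet had the lesion, and the listed data would not separate the two.

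The direction terms also look inconsistent. The test is introduced through eversion, positivity is set on inversion or internal rotation, and the technique text pairs eversion with internal rotation.

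**Working it through.** The documents give no accuracy, prevalence, sample size, power or target effect, so there is no planned figure to reproduce. Every input below is assumed and serves only to show scale.

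**1. Could the combining rule change who enters?** Let each joint be restricted with probability p, and let the two correlate at phi.

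- Both = p² + phi·p(1−p)
- Either = 2p − both
- Share of either-joint admissions that a both-joints rule would exclude = 1 − both/either

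| p | phi | both | either | excluded |
|---|---|---|---|---|
| 0.3 | 0.2 | 0.132 | 0.468 | 72% |
| 0.4 | 0.6 | 0.304 | 0.496 | 39% |
| 0.6 | 0.8 | 0.552 | 0.648 | 15% |

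So the choice of rule can matter for who enters.

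**2. Could it change how many enrolled feet have the lesion?** Assume 50% prevalence, 0.8 sensitivity and specificity per joint, and independent joints.

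- Either joint: sensitivity 1 − 0.2² = 0.96 and false-positive rate 1 − 0.8² = 0.36. Admitted 0.5(0.96 + 0.36) = 66%, of whom 0.48/0.66 = 73% have the lesion.
- Both joints: sensitivity 0.8² = 0.64 and false-positive rate 0.2² = 0.04. Admitted 0.5(0.64 + 0.04) = 34%, of whom 0.32/0.34 = 94% have it.

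This compares two different rules. It does not compare a written rule with an unwritten one. If the assessor already works by one of them consistently, writing it down admits the same feet.

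**3. What would dilution cost?** Take the whole test at 0.8 sensitivity and specificity. The share with the lesion is 0.8·prev / [0.8·prev + 0.2·(1−prev)]. Assume feet without the lesion do not respond, so that observed d = share × 0.50. Use a two-sample t test on change at two-sided 0.05, with 64 per arm because that size gives 80% power at d = 0.50.

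| prevalence | share | observed d | power at 64 per arm | per arm for 80% |
|---|---|---|---|---|
| (no dilution) | 1.00 | 0.50 | 80% | 64 |
| 0.7 | 0.90 | 0.45 | 71% | 79 |
| 0.5 | 0.80 | 0.40 | 61% | 100 |
| 0.3 | 0.63 | 0.315 | 42% | 160 |

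**4. How firm is that range?** Two changes of assumption move it noticeably.

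- Accuracy 0.9 at 70% prevalence: share 0.63/(0.63 + 0.03) = 0.955, d about 0.48, power about 76%.
- Feet without the lesion respond half as much, at share 0.63: d = 0.50 × (0.63 + 0.37 × 0.5) = 0.41, power about 63% instead of 42%. The general objective also gives a neurophysiological rationale through sensory input from the foot, so some response in such feet is not excluded.

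**5. Does the loss belong to the gap in the text?** No. Step 3 takes 0.8 accuracy as given and never uses the combining rule from step 1. A fully specified test with the same accuracy would lose the same power. A kappa between two assessors measures agreement, and two readers can agree and both be wrong. The documents contain no reference standard for the lesion beyond this test.

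**6. Is the comparison between arms affected?** The test is at step 4 and allocation at step 6. The same assessor applies the same test before any arm is known, so misclassified feet are spread by chance across both arms.

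**The case for a change.** The strongest case for a change is that a second team could not reproduce the enrolled population from the text, that step 2 of the working shows the unstated rule can matter, and that the remedy is cheap: a sentence, some database fields and a second short test. It adds that an ambiguous entry test leaves a null result hard to interpret.

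Part of this stands. The protocol is thin here, and a report of the trial should say how the two joints were judged. The direction terms do not sit together: if eversion goes with internal rotation, as the technique text has it, a rule that names inversion and internal rotation as alternatives needs explaining. Those passages must be reconciled. I take no view on which term is right.

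The rest does not carry the point. The positivity sentence is written for the scaphoid, and the two compressions are how the assessor locates the restriction, so any such restriction found is a natural reading, though not an explicit one. A trained assessor can apply that consistently. A second blinded reader needs another trained person at screening and another handling of the foot just before baseline, and would still not show whether the lesion was truly present. Recording the result by joint is reasonable housekeeping but changes no planned analysis. Nor do the documents establish that no other measure could reveal a mis-screened foot, since a clinical history is taken at step 3 and the inclusion criteria are not listed.

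**Conclusion.** No change to the plan is called for. This is a gap in description that a trained assessor fills in practice, in a test applied identically to both arms before randomisation. Bias between arms from this source is nil. Loss of power is possible but cannot be sized from the documents: the illustrative 42–71% rests on an assumed accuracy of 0.8, prevalence of 30–70%, no response in feet without the lesion, a d of 0.50 that the SAP offers only as a label for interpretation, and a sample size the documents never state. With a nearly perfect test the loss is close to nil. Whatever its true size, it comes from the accuracy of manual testing, which neither clearer wording nor an agreement statistic would improve. The mismatch in direction terms is real and must be reconciled by the investigators, but it is a matter of wording with no shown effect on the planned comparison.

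### Do the inversion and eversion labels in the scaphoid entry test contradict the technique, so that the wrong feet could be enrolled?

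*Combined protocol and SAP*

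**What the plan says.** Study sequence step 4 has the assessor examine the right scaphoid and "verify that it is in osteopathic external rotation dysfunction, if this dysfunction is not present, the subject will be excluded from the study". The condition is stated in rotation terms only.

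Scaphoid mobility assessment describes how this is done. It introduces a manual test "for which the eversion restriction of the first ray of the foot will be evaluated". With the foot held, "he checks the direction of the restriction by performing a compression to test the talus-scaphoid", followed by a lighter compression for the neighbouring joint. The decision rule is "If there is restriction of scaphoid inversion or internal rotation movement, the test is positive", and a positive result is read as "indicating that the scaphoid is in an osteopathic external rotation lesion".

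Osteopathic tug manipulation of the scaphoid names an external rotation lesion as its target. The operator sets up by "bringing the sole of the foot into eversion, thus bringing the scaphoid into internal rotation, i.e. in the direction of correction", and the thrust adds an "increase of the correction parameter towards scaphoid internal rotation".

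Randomisation comes later, at step 6: "The patient will go to an adjoining room with the auditor to carry out the randomisation process".

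**The concern.** Three sentences use an inversion or eversion label, and they do not obviously match. The test says it examines restricted eversion, yet restricted inversion makes it positive. The rule sets inversion beside internal rotation, while the technique obtains internal rotation through eversion.

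This is the eligibility rule, and the mobility section is its only operational definition. If inversion and internal rotation were alternatives, and were also opposite movements as the technique's coupling might suggest, a foot with restricted inversion and free internal rotation would test positive. Such a foot would lack the restriction that the manipulation is meant to release. The study population would be mixed and any effect could be diluted. No sentence says that the direction found is recorded, so a reader might be unable to check this afterwards.

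**Working it through.** The documents give no figure on this point, so the check is a comparison of wording.

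**Rotation terms**

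| Place | Statement |
|---|---|
| Step 4 | external rotation dysfunction required |
| Test, decision rule | internal rotation restricted |
| Test, interpretation | external rotation lesion |
| Technique, aim | external rotation lesion |
| Technique, set-up | internal rotation is the direction of correction |
| Technique, taking up slack | internal rotation increased |
| Technique, thrust | towards internal rotation |

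These seven statements describe one picture: a scaphoid held in external rotation, limited towards internal rotation, and moved towards internal rotation. There is one loose phrase. The technique aim also speaks of releasing a restriction in external rotation, which taken alone could mean that external rotation is the limited movement. It agrees with the rest when read as a joint fixed in external rotation, and the lesion named in the same sentence supports that reading.

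**Inversion and eversion labels**

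| Place | Segment | Label | Rotation named with it |
|---|---|---|---|
| Test, opening | first ray | eversion | none |
| Test, decision rule | scaphoid | inversion | internal |
| Technique, set-up | sole | eversion | internal (of the scaphoid) |

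Suppose one convention covers all three segments. Pairing internal rotation with eversion leaves one of the three statements unmatched (the decision rule). Pairing it with inversion leaves two unmatched (the test opening and the technique). Neither pairing fits all three. That result depends on the shared convention, which the documents do not state. It also has to infer a rotation for the first-ray sentence, which names none.

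If labels are specific to the segment, one reading fits everything: eversion of the first ray or sole goes with inversion and internal rotation of the scaphoid. The documents do not state this convention either. Because it is available, though, the three sentences do not prove a contradiction.

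**Consequences for eligibility**

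There are two open questions: whether the labels share one convention, and whether the word joining inversion to internal rotation gives a second name or a second criterion.

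| | Two names for one movement | Two separate criteria |
|---|---|---|
| Labels specific to the segment | same feet enrolled | same feet enrolled, since both terms point the same way |
| One convention for all segments | same feet enrolled; one name is mismatched | restricted inversion alone could admit a non-target foot |

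Only one of the four combinations changes who is enrolled. In that cell the assessor would also have to find internal rotation free and still record an external rotation dysfunction for step 4.

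**Effect on the comparison**

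The test is step 4, the baseline platform recording is step 5 and allocation is step 6. Any looseness at entry therefore applies before either group exists and cannot favour one of them.

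**The case for a change.** The strongest case for a change is that a reader should not have to supply a convention. The decision rule does contain the word inversion, step 4 relies on that rule, and agreement among the rotation terms does not remove the word. A second assessor or a replicating team could not tell from the text alone whether restricted inversion by itself qualifies. The technique itself links sole to scaphoid, so treating the labels as connected is reasonable. The remedy would be cheap.

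Part of this stands. The terms are undefined across the three segments, and a sentence saying which segment each label describes, and whether the rule names one movement or two, would help the reader.

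The step from unclear wording to a wrong eligibility rule does not stand. The rule has a single noun for the movement and leads to a single conclusion, so two names for one motion is the more natural reading. On that reading only a naming mismatch is left. Unidiomatic English elsewhere in the document makes a translation slip plausible, though this cannot be proved.

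The recording point is also weak. The six listed outputs (two oscillations, ellipse area, support area, load share, maximum pressure point) come from the platform, so a manual finding would not be among them. Steps 3 and 9 provide for a clinical history and a database without listing fields. In rotation terms every enrolled participant must show the same finding, so a direction field would be nearly constant.

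**Conclusion.** No change to the plan follows. The labels are loosely used, but a contradiction is not shown, and the entry condition is set in rotation terms that agree with the test's conclusion and with the thrust.

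Enrolment is affected in one of four combinations of readings, and that combination needs both a shared labelling convention and two separate criteria. Even there, the consequence would be a more mixed population and possibly a diluted effect, not bias between groups. Its size cannot be calculated, because the documents give no sample size, power or share of feet affected.

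The conclusion rests on two assumptions: that the assessor applies step 4 in the rotation terms in which it is written, and that the loose phrase in the technique aim means fixed in external rotation. Which inversion or eversion label is apt for each segment is for the investigators to say. If they tidy the wording, or explain how the rule was applied should enrolment have begun, that is a clarification of terms and alters neither the design nor the analysis.
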